12.3 Contraception Requirements

Contraception for Pediatric Male Subjects of Reproductive Potential

Male children/adolescents in the following categories are not considered of reproductive potential:

- 1. Tanner stage 1 development
- 2. Documented surgically sterile

Documentation from the site personnel's review of the male subject's medical records, medical exam and medical history interview is necessary.

Contraception guidance for male children/adolescents of reproductive potential:

- Male children/adolescents of reproductive potential (Tanner Stage 2 and above) receiving non-genotoxic agents should use a condom during treatment and for 3 weeks + 5 × half-life of drug after last dose.
- Male children/adolescents of reproductive potential receiving genotoxic agents should use a condom during treatment and for 90 days + 5 × half-life of drug after last dose.
- Male participants should inform their female partners that they are participating in a clinical trial and effective methods of contraception should be used.
- Female partners of male subjects who have not undergone bilateral orchiectomy should consider use of highly effective methods of contraception until the end of relevant systemic exposure, as defined above.

Contraception for Pediatric Female Subjects of Childbearing Potential

Female children/adolescents in the following categories are not considered of childbearing potential:

- 1. Pre-menarchal
- 2. Documented surgically sterile (hysterectomy, bilateral salpingectomy, bilateral oophorectomy)

Documentation from the site personnel's review of the female subject's medical records, medical exam and medical history interview is necessary.

Contraception guidance for female children/adolescents of childbearing potential:

- Female children/adolescents of childbearing potential receiving non-genotoxic agents should use highly effective contraception during treatment and for 30 days after last dose.
- Female children/adolescents of childbearing potential receiving genotoxic agents should use contraception during treatment and for 180 days + 5 × half-life of drug after last dose.
- Pregnancy testing for female children/adolescents of childbearing potential
 - o At all on-site visits and 30 days after end of relevant systemic exposure

Sponsor: APGD - CONFIDENTIAL -

EudraCT number 2016-001767-37

One of the highly effective methods of contraception listed below is required at the time of informed consent and until the end of relevant systemic exposure as defined above.

ISN/Protocol: 178-CL-204

Highly Effective Birth Control Methods-failure rate < 1%/year

- 1. Combined estrogen and progestogen containing hormonal contraception
 - a. Oral
 - b. Intravaginal
 - c. Transdermal-Patch
 - d. Injectable-Cyclofem, Mesigyna
 - e. Intrauterine device
 - f. Intrauterine hormone-releasing system
- 2. Progestogen-only hormonal contraception
 - a. Oral
 - b. Injectable-DMPA-IM or -SC
 - c. Implantable-Norplant
- 3. Bilateral tubal occlusion
- 4. Vasectomized male partner
- True abstinence*

*True abstinence: When this is in line with the preferred and usual lifestyle of the subject. Periodic abstinence (e.g., calendar, ovulation, symptothermal, post-ovulation methods) and withdrawal are not acceptable methods of contraception. Sexual abstinence is considered a highly effective method only if defined as refraining from heterosexual intercourse during the entire period of risk associated with the study drug. It is not necessary to use any other method of contraception when complete abstinence is elected.

Birth control methods considered unacceptable:

- 1. Periodic abstinence (calendar, symptothermal, post-ovulation methods)
- Withdrawal (coitus interruptus)
- 3. Spermicides only
- 4. Lactational amenorrhea

ISN/Protocol: 178-CL-204

12.4 Adverse Events: Definitions and Procedures for Recording, Evaluating, Follow-up and Reporting

12.4.1 Definition of Adverse Events

An AE is any untoward medical occurrence in a subject administered an IP, and which does not necessarily have to have a causal relationship with this treatment. An AE can therefore be any unfavorable and unintended sign (including an abnormal laboratory finding), symptom, or disease (new or exacerbated) temporally associated with the use of IP whether or not considered related to the IP.

12.4.1.1 Abnormal Laboratory Findings

Any abnormal laboratory test result (e.g., hematology, biochemistry or urinalysis dipstick) or other safety assessment (e.g., vital signs, physical examination, ECGs or radiographic scans), including those that worsen from baseline should be considered to be reported as an (S)AE.

Any abnormal laboratory finding or other abnormal safety assessment, which is associated with the underlying disease or with concomitant medication, will not be considered an AE unless judged by the investigator to be more severe than expected for the subject's condition or not associated with the known side effects of the concomitant medication. Additionally, minor laboratory deviations or fluctuations outside of normal ranges of preexisting disease(s) or condition(s) present or detected at the start of the study that do not worsen and/or that are not reproducible with re-testing will not to be considered an AE.

Repeating an abnormal laboratory test or other safety assessment, in the absence of any of the above criteria, does not constitute an AE. Any abnormal test result that is determined to be an error does not require reporting as an AE.

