2.1.3 Summary of Key Safety Information for Investigational Product(s)

Mirabegron has not been approved or marketed for use in pediatric subjects.

Detailed reference safety information (RSI) can be found in the Investigator's Brochure for mirabegron.

- CONFIDENTIAL -

Mirabegron has been approved in more than 81 countries worldwide. In adults, the safety of mirabegron treatment has been well characterized in 5863 subjects (95% with OAB) in the phase 2/3 registration studies treated with mirabegron at doses ranging from 25 to 200 mg once daily. Identified risks include increased heart rate and tachycardia, hypersensitivity reactions, increased blood pressure and urinary retention. Potential risks include QT prolongation, urinary tract infection (UTI), fetal disorders after exposure during pregnancy and events induced by concomitant treatment with cytochrome P450 2D6 (CYP2D6) substrates with a narrow therapeutic index. The risks of QT prolongation, increased heart rate or increased blood pressure are greater with increasing exposure at supratherapeutic doses and can be mitigated with optimal dose selection. The maximum therapeutic dose of mirabegron based on the overall benefit-risk is 50 mg once daily in adults.

ISN/Protocol: 178-CL-204

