7.2.3 Vital Signs and Electrocardiograms

7.2.3.1 Clinic-measurement of Vital Signs and Electrocardiograms

Blood pressure (systolic blood pressure [SBP] and diastolic blood pressure [DBP]), pulse, and routine 12-lead ECG measurements will be taken as indicated in the Schedule of Assessments [Table 1].

The preferred method of measurement is via the auscultatory technique. If this method is not available at the study site, measurements will be per standard clinic practices. Single measurements of blood pressure, pulse, body temperature and ECGs will be measured in the sitting position (when possible, otherwise supine, but always in the same position). Subject should have been calm and without distress for at least 5 minutes. Preferably, the right arm should be used to measure vital signs. Body temperature will be measured with an ear thermometer as per standard of care. Clinic measurements will be used to assess eligibility.

For ECGs, dates and times may be generated by the machine's internal clock and are considered source data. The results are to be interpreted by qualified personnel in real time for the management of the subjects' clinical condition. The principal investigator/designee will initial and date and provide his/her clinical interpretation on each report. Any abnormalities must be evaluated in clinical context (based on subject's medical history and concomitant medication) and the investigator should determine if it is clinically significant. The results (normal, abnormal not clinically significant, abnormal clinically significant) are to be recorded in the eCRFs.

The original print-out and an electronic copy of all scheduled and unscheduled ECG tracings should be maintained on site as source data.

Clinic measurements will be used to assess eligibility. Clinically relevant adverse changes in vital signs and ECGs will be recorded as an AE (see [Appendix 12.4.1 Definition of Adverse Events]).

- CONFIDENTIAL -

ISN/Protocol: 178-CL-204

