12.4.3 Criteria for Causal Relationship to Investigational Product

A medically qualified investigator is obligated to assess the relationship between IP and each occurrence of each (S)AE. This investigator will use medical judgment as well as the reference safety information [Section 2.1.3 Summary of Key Safety Information for Investigational Product(s)] to determine the relationship. The causality assessment is 1 of the criteria used when determining regulatory reporting requirements.

The investigator is requested to provide an explanation for the causality assessment for each (S)AE and must document in the medical notes that he/she has reviewed the (S)AE and has provided an assessment of causality.

Following a review of the relevant data, the causal relationship between the IP and each (S)AE will be assessed by answering "yes" or "no" to the question "Do you consider that there is a reasonable possibility that the event may have been caused by the IP?"

When making an assessment of causality, the following factors are to be considered when deciding if there is evidence and/or arguments to suggest there is a "reasonable possibility" that an (S)AE may have been caused by the IP (rather than a relationship cannot be ruled out) or if there is evidence to reasonably deny a causal relationship:

- Has the subject been administered IP?
- Plausibility (i.e., could the event have been caused by the suspect drug? Consider biologic and/or pharmacologic mechanism, half-life, literature evidence, drug class, preclinical and study data, etc.)
- Dechallenge/dose reduction/rechallenge:
 - Dechallenge: did the (S)AE resolve or improve after only stopping the dose of the suspect drug without any treatment?
 - Dose reduction: did the (S)AE resolve or improve after reducing the dose of the suspect drug?

Sponsor: APGD ISN/Protocol: 178-CL-204 EudraCT number 2016-001767-37

- CONFIDENTIAL -

• Rechallenge: did the (S)AE reoccur if the suspected drug was reintroduced after having been stopped?

- Laboratory or other test results: a specific lab investigation supports the assessment of the relationship between the (S)AE and the IP (e.g., based on values pre-, during and post-treatment)
- Available alternative explanations independent of IP exposure; such as other concomitant drugs, past medical history, concurrent or underlying disease, risk factors including medical and family history, season, location, etc., and strength of the alternative explanation

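### Appendix 12.4.1.1 lets attribution to a concomitant medicine decide whether an abnormal laboratory, vital-sign or ECG finding is an adverse event, contrary to the AE definition in 12.4.1 and to Sections 7.2.2 and 7.2.3.1

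*Protocol*

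**What the plan says.** Protocol Appendix 12.4.1 defines an AE broadly: "An AE can therefore be any unfavorable and unintended sign (including an abnormal laboratory finding), symptom, or disease (new or exacerbated" and so on, provided it is "temporally associated with the use of IP whether or not considered related to the IP". Cause plays no part in the definition.

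Appendix 12.4.1.1, directly below, opens in the same spirit. It covers abnormal laboratory results and any "other safety assessment (e.g., vital signs, physical examination, ECGs or radiographic scans), including those that worsen from baseline should be considered to be reported". The reporting in question is (S)AE reporting. Its next paragraph takes some of these back out: an abnormal finding "which is associated with the underlying disease or with concomitant medication, will not be considered an AE unless judged by the investigator" to qualify on one of two grounds, namely that it is "more severe than expected for the subject's condition or not associated with the known side effects of the concomitant medication".

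The main body has no such exemption. Section 7.2.3.1 says: "Clinically relevant adverse changes in vital signs and ECGs will be recorded as an AE". Section 7.2.2 applies the same rule to clinically relevant laboratory changes, and SAP Section 5.4.3 repeats it.

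Appendix 12.4.3 already has a place for the role of another medicine. Among the factors in the causality assessment it lists "Available alternative explanations independent of IP exposure; such as other concomitant drugs".

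**The concern.** Whether an event is an AE and what caused it are separate questions. The protocol keeps them apart in 12.4.1 and 12.4.3, but 12.4.1.1 merges them: once an investigator puts a finding down to a concomitant medicine, the default is that it is not an AE at all. The suspected cause then decides whether the record exists, when it should be one attribute of the record.

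This matters because several AEs of special interest in Section 7.3.6 usually come to light as abnormal assessments: increased blood pressure, QTc prolongation, increased heart rate and hepatotoxicity. The 24-hour reporting in that section applies to AEs of special interest. The SAP builds its treatment-emergent AE tables, and its search for AEs of interest, from recorded AEs. A finding that never becomes an AE reaches none of these.

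**Working it through.** No arithmetic applies; the point is textual. Take a hypothetical subject on a permitted concomitant medicine known to raise blood pressure. The subject has a clinically relevant rise during treatment, and the investigator puts it down to that medicine.

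| Provision | Test applied | Is the rise an AE? |
|---|---|---|
| Protocol 12.4.1 | Unfavourable sign, temporally associated with IP, any cause | Yes |
| Protocol 7.2.3.1 | Clinically relevant adverse change in a vital sign | Yes |
| Protocol 12.4.1.1 | Associated with a concomitant medicine and within its known side effects | No, unless judged worse than the subject's condition would lead one to expect |

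The same clash arises for an ECG change (7.2.3.1) and for a laboratory change (7.2.2).

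The exemption has two limits. A finding outside the medicine's known side effects returns to AE status, and so does one judged too severe. But the severity limit is tied to the subject's condition, not to the usual size of the medicine's effect, so it is unclear whether it catches a marked but known drug effect.

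If 12.4.1.1 is followed, the consequences are these:

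1. **Expedited reporting.** Protocol 7.3.6 sends AEs of special interest to the sponsor within 24 hours. With no AE, nothing triggers the report.
2. **AE tables.** SAP 5.4.1 defines a treatment-emergent AE as an AE, so the finding is absent from the SAP 6.5.1 tables.
3. **AEs of interest.** SAP 5.4.1 finds these by searching preferred terms of recorded AEs, so the finding is absent there for blood pressure, QT and arrhythmia. Hepatotoxicity is on the Protocol 7.3.6 list but not on the SAP's list. For liver findings the loss is therefore items 1 and 2.
4. **Measured values.** These remain. Laboratory data are summarised and listed (SAP 6.5.2), and liver thresholds use the highest central-laboratory value (6.5.2.2). Blood pressure and pulse have shift tables and potentially-clinically-relevant flags (6.5.3.1, 6.5.3.2), and QTcF has categorical summaries (6.5.4). Under Protocol 7.2.3.1 the ECG interpretation goes into the eCRF, and under Appendix 12.5 confirmed moderate or severe liver abnormalities go on a dedicated form.

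Item 4 is a substantial backstop, but an incomplete one. SAP 6.5.3.2 only lists extra home blood pressure readings, so a rise seen only in one of those would be tabulated only as an AE. The liver threshold table uses central-laboratory values, whereas Protocol Appendix 12.13 allows local sampling in a crisis. The rule on potential Hy's Law cases in 12.4.1.2 applies only when other causes are absent, so attribution limits it too. Value tables also carry no seriousness or causality assessment.

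**The case against.** **The data are not lost.** A reader might infer that blood pressure, pulse, QT and liver findings go unrecorded. The documents do not support that. The values are captured and analysed by treatment group whatever their AE status. The blood pressure flags can be met by measured values alone, and the blood pressure, QT and liver stopping criteria in Protocol 8.1 act on measurements. This objection stands in full and confines the point to AE and AESI reporting.

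**The exemption is narrow.** It has the two limits above, and the section opens by telling sites to consider any abnormal result for reporting. QT-prolonging drugs and moderate or strong CYP3A4/5 and P-gp inhibitors and inducers are prohibited (6.5), which shrinks the pool of relevant medicines, most clearly for QT. This stands as a limit on how often the rule would apply. It does not remove the contradiction.

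**The appendix may simply refine the main body.** Section 7.2.3.1 refers the reader to 12.4.1, and 7.2.2 leads through 7.3 to Appendix 12.4. That is a fair reading, but it would make the exemption the operative rule, and 12.4.1.1 would still contradict its own parent section.

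**Drug interactions have their own route.** A reader might infer that events are lost unevenly between arms, because mirabegron could raise exposure to a permitted CYP2D6 substrate and the result would pass as that drug's side effect. The documents do not support this. The potential risk that the protocol names is limited to "events induced by concomitant treatment with cytochrome P450 2D6 (CYP2D6) substrates with a narrow therapeutic index"; sensitive substrates of that kind are prohibited, investigators are blinded, and a suspected interaction must be reported within 24 hours under 12.4.6.7. That route works only if someone suspects an interaction, but nothing here establishes a differential loss.

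**The text followed an agency comment.** The amendment summary (Section 13) links the revision of 12.4.1.1 to an agency comment on laboratory values. The comment itself is not given, so it cannot show that this exemption was requested. The sponsor should check.

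**Conclusion.** The contradiction is real and is in current text. Appendix 12.4.1.1 makes AE status depend on attribution to a concomitant medicine, whereas 12.4.1, 7.2.2 and 7.2.3.1 do not. Findings in the special-interest categories can therefore miss expedited reporting and the AE tables, although their measured values are still collected and summarised or listed. The conclusion assumes only that sites apply 12.4.1.1 as written.

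The size of the loss cannot be estimated, because the documents give no rate at which findings are attributed to concomitant medicines. A reader might try to size it from Study 178-CL-206A, where 1 of 78 patients met the criteria for a hypertension TEAE. Applied to the planned 108 mirabegron subjects (92 + 16), that gives 108 × 1/78 = 1.4 events. The figure should not be used. That study was open-label, in neurogenic patients, and ran for up to 52 weeks; scaling by time alone gives 1.4 × 12/52 = about 0.3. The one event was judged unrelated to study drug. Above all, it is a rate of events, not of attribution to other medicines.

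The point should be corrected because the rule is explicit, it reaches the events the protocol most wants to see, and the correction is cheap.

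**What to change.** In Protocol Appendix 12.4.1.1:

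- Delete the reference to concomitant medication in the exemption, and the matching closing condition about that medicine's known side effects.
- State that clinically relevant new or worsened laboratory, vital-sign and ECG findings are recorded as AEs, in line with 7.2.2 and 7.2.3.1.
- Direct investigators to record any suspected role of a concomitant medicine in the causality explanation required by 12.4.3.

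If the sponsor keeps some form of exemption, it should at least exclude the Section 7.3.6 categories. The new wording should be checked against the agency comment cited for the amendment. The underlying-disease part of the same sentence also sits awkwardly with 12.4.1. Section 7.3.5 deals separately with disease progression, and the two should be read together when the text is revised.

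The cost is a wording change and a few more AE records. No new assessments are needed.

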12.4.1.2 Potential Cases of Drug-induced Liver Injury

Refer to [Appendix 12.5 Liver Safety Monitoring and Assessment] for detailed instructions on drug induced liver injury. Abnormal values in AST and/or ALT concurrent or with abnormal elevations in TBL that meet the criteria outlined in [Appendix 12.5 Liver Safety Monitoring and Assessment], in the absence of other causes of liver injury, are considered potential cases of drug-induced liver injury (potential Hy's Law cases) and are always to be considered important medical events and reported per [Appendix 12.4.5 Reporting Procedures for Serious Adverse Events].

12.4.2 Definition of Serious Adverse Events

An AE is considered "serious" if, in the view of either the investigator or sponsor, the event:

- Results in death
- Is life-threatening (An AE is considered "life-threatening" if, in the view of either the investigator or sponsor, its occurrence places the subject at immediate risk of death; it does not include an AE that, had it occurred in a more severe form, might have caused death)

ISN/Protocol: 178-CL-204

- Results in persistent or significant disability/incapacity or substantial disruption of the ability to conduct normal life functions
- Results in congenital anomaly, or birth defect
- Requires inpatient hospitalization (except for planned procedures as allowed per study) or leads to prolongation of hospitalization (except if prolongation of planned hospitalization is not caused by an AE)
- Other medically important events (defined in paragraph below)

Medical and scientific judgment should be exercised in deciding whether expedited reporting is appropriate in other situations, such as important medical events that may not be immediately life-threatening or result in death or hospitalization, but may jeopardize the subject or may require intervention to prevent 1 of the other outcomes listed in the definition above. These events, including those that may result in disability/incapacity, usually are considered serious. Examples of such events are intensive treatment in an emergency room or at home for allergic bronchospasm, blood dyscrasias or convulsions that do not result in hospitalization, or development of drug dependency or drug abuse.

12.4.3 Criteria for Causal Relationship to Investigational Product

A medically qualified investigator is obligated to assess the relationship between IP and each occurrence of each (S)AE. This investigator will use medical judgment as well as the reference safety information [Section 2.1.3 Summary of Key Safety Information for Investigational Product(s)] to determine the relationship. The causality assessment is 1 of the criteria used when determining regulatory reporting requirements.

The investigator is requested to provide an explanation for the causality assessment for each (S)AE and must document in the medical notes that he/she has reviewed the (S)AE and has provided an assessment of causality.

Following a review of the relevant data, the causal relationship between the IP and each (S)AE will be assessed by answering "yes" or "no" to the question "Do you consider that there is a reasonable possibility that the event may have been caused by the IP?"

When making an assessment of causality, the following factors are to be considered when deciding if there is evidence and/or arguments to suggest there is a "reasonable possibility" that an (S)AE may have been caused by the IP (rather than a relationship cannot be ruled out) or if there is evidence to reasonably deny a causal relationship:

- Has the subject been administered IP?
- Plausibility (i.e., could the event have been caused by the suspect drug? Consider biologic and/or pharmacologic mechanism, half-life, literature evidence, drug class, preclinical and study data, etc.)
- Dechallenge/dose reduction/rechallenge:
 - Dechallenge: did the (S)AE resolve or improve after only stopping the dose of the suspect drug without any treatment?
 - Dose reduction: did the (S)AE resolve or improve after reducing the dose of the suspect drug?

Sponsor: APGD ISN/Protocol: 178-CL-204 EudraCT number 2016-001767-37

- CONFIDENTIAL -

• Rechallenge: did the (S)AE reoccur if the suspected drug was reintroduced after having been stopped?

- Laboratory or other test results: a specific lab investigation supports the assessment of the relationship between the (S)AE and the IP (e.g., based on values pre-, during and post-treatment)
- Available alternative explanations independent of IP exposure; such as other concomitant drugs, past medical history, concurrent or underlying disease, risk factors including medical and family history, season, location, etc., and strength of the alternative explanation
- Finally, judging which are more likely based on all the above contents, factors of reasonable possibility or confounding factors, comprehensive judgment of plausible temporal relationship between exposure to the IP and (S)AE onset and/or resolution will be provided. Did the (S)AE occur in a reasonable temporal relationship to the administration of the IP?

There may be situations in which an SAE has occurred and the investigator has minimal information to include in the initial report to the sponsor. However, it is very important that the investigator always assesses causality for every event before the initial transmission of the SAE data to the sponsor. With limited or insufficient information about the event to make an informed medical judgment and in absence of any indication or evidence to establish a causal relationship, a causality assessment of "no" is to be considered. In such instance, the investigator is expected to obtain additional information regarding the event as soon as possible and to re-evaluate the causality upon receipt of additional information. The medically qualified investigator may revise his/her assessment of causality in light of new information regarding the SAE and shall send an SAE follow-up report and update the electronic data source with the new information and updated causality assessment.

